9.3 Supportive Care and Concurrent Treatments

9.3.1 Treatments: Prophylactic medications should be routinely administered in combination with Dexamethasone. Individualization is required, as some patients require no prophylaxis therapy, while other patients require intensive therapy. The particular choice of prophylactic therapy will be at the discretion of the treating physician investigator. We recommend patients receive omeprazole 20 mg once daily as gastritis prophylaxis, docusate 100mg tablet twice daily for constipation prophylaxis, Bactrim DS 1 tablet once daily for *Pneumocystis carinni* pneumonia prophylaxis beginning with cycle 2 of either BiRd or Rd therapy, and mycelex troches 10mg four to five times daily as needed for oral thrush prophylaxis. See Section 9.1 for thromboembolic prophylaxis using aspirin, warfarin or coumadin.

9.3.2 Lytic Bone Lesions: Patients with lytic bone lesions, if able to, should receive standard of care treatment in routine multiple myeloma management, such as IV bisphosphonates, as determined by the investigator. It is preferred that investigators use the same route of bisphosphonate therapy for all subjects at their sites (if applicable).

9.3.3 Hematopoietic support: Thrombocytopenia should be treated conservatively. In the absence of bleeding, platelet transfusions should only be given for a platelet count below 10,000. If the patient develops bleeding, platelet transfusions should be administered in accordance with standard of practice, usually maintaining a platelet count $\geq 50,000/\text{mm}^3$. Febrile neutropenia is a life-threatening complication requiring hospitalization and urgent broad-spectrum antibiotics. Hematopoietic growth factors may be used according to Table 2: Dose Modification Instructions. Such cases will be evaluated individually to determine the toxicity grade. Symptomatic anemia should be treated with appropriate red blood cell support and transfusion is recommended if the hemoglobin falls below 8 g/dl. Recombinant erythropoietin may be used with concurrent anticoagulation, as described above in section 9.1, if desired by the patient's local physician.

9.3.4 Radiotherapy: Patients who require localized external beam radiotherapy or surgery at the time of protocol screening should receive it before study entry. Patients may receive radiotherapy or surgery during the study if required to treat a pathological fracture, cord compression, or associated pain that was present prior to study entry. Patients who require radiotherapy or surgery to treat pathological fractures related to a new growth of myeloma, cord compression, or associated pain will be considered to have progression of disease and will be removed from study. Patients may receive radiation therapy or surgery for the treatment of a plasmacytoma that was present prior to study entry only if the plasmacytoma is not considered a target lesion to assess response.

9.3.5 Prohibited Concomitant Therapy: Concomitant use of sargramostim (GM-CSF), other anti-cancer therapies, or other investigational agents is not permitted while subjects

are receiving study drug during the treatment phase of the study. Agents that alter the QTc will be discouraged particularly in patients receiving clarithromycin. See Appendix VII

9.4 Day One Dosing Guidelines

A new cycle of treatment may begin on a scheduled Day 1 if any therapy related adverse events have resolved to an acceptable grade (see Section 9.3, Dose Modifications). If not, the patient should be evaluated at least at weekly intervals until resolution of toxicities. If start of new cycle is delayed more than 4 weeks, the patient will be removed from the protocol. The patient will also be directed to take the following prophylactic medicines: 1) omeprazole at a dose of 20mg once daily; 2) Bactrim at a dose of one DS tab once daily (or equivalent *Pneumocystis jiroveci* prophylaxis; patients may start at cycle 2 if preferred by treating physician); 3) aspirin at a dose of 81 mg once daily (or other equivalent anti-thrombotic therapy).

9.5 Instruction for initiation of a new cycle

A new course of treatment may begin on the scheduled Day 1 of a new cycle if:

- Absolute neutrophil count (ANC) ≥ 750 cells/mm³
- Platelets count $\geq 50,000$ /mm³
- Any other drug-related adverse events that may have occurred have resolved to \leq grade 2 severity.

If these conditions are not met on Day 1 of a new cycle, the subject will be evaluated weekly and a new cycle of treatment will not be initiated until the toxicity has resolved as described above. If the toxicity does not resolve within four weeks, the patient will be taken off the study. If the dosing of clarithromycin, lenalidomide or dexamethasone was halted during the previous cycle and was restarted with a one-level dose reduction without requiring an interruption for the remainder of the cycle, then that reduced dose will be initiated on Day 1 of the new cycle. If the dosing of clarithromycin, lenalidomide or dexamethasone was omitted for the remainder of the previous cycle or if the new cycle is delayed due to toxicity newly encountered on the scheduled Day 1, then the new cycle will be started with dose modifications as described in Section 9.6 and Table 2.

If the start of a new cycle is delayed more than 4 weeks, the patient will be removed from the protocol.

9.6 Dose Modification

Doses of study medications will be modified for toxicity as listed below in Tables 1, 2a, and 2b. Doses must be adjusted for adverse events deemed related to study drug by the investigator. Doses may be adjusted for adverse events related to study medications not listed below at the discretion of the investigator.

Unless otherwise noted, other drugs in the regimen should be continued when the dosing of one or more drugs is delayed due to toxicity.

During BiRd therapy, if toxicity occurs that would indicate an interruption in treatment, the toxicity should be attributed to one or more drugs in the BiRD regimen and dose modifications instituted as instructed in the “Action” column of the table below based on attribution. During maintenance therapy, if toxicity occurs that would indicate a lenalidomide dose modification, toxicity should be attributed to lenalidomide and dose modifications instituted as instructed in the “Action” column of the table below based on attribution.

Table 1: Dose Reduction Steps:

Lenalidomide Dose Reduction

Starting Dose	Lenalidomide PO 25mg/day on days 1-21 of a 28 day cycle
Dose Level -1	Lenalidomide PO 15mg/day on days 1-21 of a 28 day cycle
Dose Level -2	Lenalidomide PO 10 mg/day on days 1-21 of a 28 day cycle
Dose Level -3	Lenalidomide PO 5 mg/day on days 1-21 of a 28 day cycle
Dose Level -4	Lenalidomide PO 5 mg every other day for on days 1-21 of a 28 day cycle

Dexamethasone Dose Reduction

Starting Dose	40 mg PO on days 1, 8, 15 and 22 of a 28 day cycle
Dose Level -1	20 mg PO on days 1, 8, 15 and 22 of a 28 day cycle
Dose Level -2	8 mg PO on days 1, 8, 15 and 22 of a 28 day cycle
Dose Level -3	8 mg PO on days 1 and 15 of a 28 day cycle
Dose Level -4	4 mg PO on days 1 and 15 of a 28 day cycle

Clarithromycin Dose Reduction

Starting Dose	500 mg BID PO days 1-28 of a 28 day cycle
Dose Level -1	250 mg BID PO days 1-28 of a 28 day cycle

Dose Level -2	250 mg PO daily on days 1-28 of a 28 day cycle
Dose Level -3	250 mg PO daily on days odd days of a 28 day cycle
Dose Level -4	Discontinue drug

Table 2a: RD Dose Modification Instructions

Toxicity	NCI Toxicity Grade	Action
Neutropenia	≥ Grade 3 with fever (temperature ≥ 38.5° C)	
 • Hold (interrupt) lenalidomide. • Follow CBC weekly. • If neutropenia has resolved to ≤ grade 2 prior to Day 21, restart lenalidomide at next lower dose level and continue through Day 21. If neutropenia is the only toxicity for which a dose reduction is required, G-CSF may be used and the lenalidomide dose maintained.
Neutropenia	Grade 4	
 • Hold (interrupt) lenalidomide. • Follow CBC weekly. • If neutropenia has resolved to ≤ grade 2 prior to Day 21, restart lenalidomide at next lower dose level and continue through Day 21. If neutropenia is the only toxicity for which a dose reduction is required, G-CSF may be used and the lenalidomide dose maintained.
Thrombocytopenia	≥ Grade 3 (platelet count < 50,000/mm ³)	
 • Hold (interrupt) lenalidomide and anti-coagulation dosing. • Follow CBC weekly. • If thrombocytopenia has resolved to ≤ grade 2 prior to Day 21, restart lenalidomide at next lower dose level and restart anti-coagulation.

Toxicity	NCI Toxicity Grade	Action
Rash (non-blistering)	\geq Grade 3	
 • Hold (interrupt) lenalidomide for remainder of cycle • Reduce lenalidomide by 1 dose level and restart next cycle.
Rash	Grade 4 non-blistering or desquamating (blistering) any Grade	
 • Discontinue lenalidomide and take patient off study
Erythema multiforme	\geq Grade 3	
 • Discontinue lenalidomide and take patient off study
Hyperthyroidism or Hypothyroidism	Any grade	
 • Omit lenalidomide remainder of cycle • Evaluate etiology and initiate appropriate therapy • Restart lenalidomide at same dose level.
Sinus bradycardia/ other cardiac arrhythmia	Grade \geq 2	
 • Hold (interrupt) lenalidomide for remainder of cycle. Follow at least weekly. • Reduce lenalidomide by 1 dose level and restart next cycle.
Sinus bradycardia/ other cardiac arrhythmia	\geq Grade 3	
 • Discontinue lenalidomide and take patient off study
Allergic reaction or hypersensitivity	\geq Grade 2	
 • Hold (interrupt) lenalidomide for remainder of cycle. Follow at least weekly. • Reduce lenalidomide by 1 dose level and restart next cycle.
Allergic reaction or hypersensitivity	\geq Grade 3	
 • Discontinue lenalidomide and take patient off study
Venous thrombosis/embolism	\geq Grade 3	
 • Hold (interrupt) lenalidomide and Start anticoagulation; restart lenalidomide at investigator's discretion (maintain dose level).
Gastritis, gastric or duodenal ulcer	\geq Grade 3	
 • Hold (interrupt) dexamethasone until \leq grade 1 • Reduce dexamethasone by 1 dose level and restart

Toxicity	NCI Toxicity Grade	Action
Edema	≥ Grade 3	
 • Reduce dexamethasone by 1 dose level • Use diuretics as needed
Confusion or mood alternations	≥ Grade 2	
 • Hold (interrupt) dexamethasone until ≤ grade 1 • Reduce dexamethasone by 1 dose level and restart
Muscle weakness	≥ Grade 3	
 • Reduce dexamethasone by 1 dose level • If symptoms persist continue to reduce dexamethasone by 1 dose level as needed.
Hyperglycemia	≥ Grade 3	
 • Reduce dexamethasone by 1 dose level • Treat with insulin or oral hypoglycemics as needed
Acute pancreatitis	≥ Grade 3	
 • Discontinue dexamethasone and patient off study.
Other non-hematologic toxicity assessed as treatment-related	≥ Grade 3	
 • Attribute toxicity to one or more drugs. Hold drug(s) attributed to toxicity for remainder of cycle. Reduce drug(s) attributed to toxicity by 1 dose level.*

Table 2b: BiRD Dose Modification Instructions

Toxicity	NCI Toxicity Grade	Action
Neutropenia	≥ Grade 3 with fever (temperature ≥ 38.5° C)	
 • Hold (interrupt) lenalidomide. • Follow CBC weekly. • If neutropenia has resolved to ≤ grade 2 prior to Day 21, restart lenalidomide at next lower dose level and continue through Day 21. If neutropenia is the only toxicity for which a dose reduction is required, G-CSF may be used and the lenalidomide dose maintained.

Toxicity	NCI Toxicity Grade	Action
Neutropenia	Grade 4	
 • Hold (interrupt) lenalidomide. • Follow CBC weekly. • If neutropenia has resolved to \leq grade 2 prior to Day 21, restart lenalidomide at next lower dose level and continue through Day 21. If neutropenia is the only toxicity for which a dose reduction is required, G-CSF may be used and the lenalidomide dose maintained.
Thrombocytopenia	\geq Grade 3 (platelet count $< 50,000/\text{mm}^3$)	
 • Hold (interrupt) lenalidomide and anti-coagulation dosing. • Follow CBC weekly. • If thrombocytopenia has resolved to \leq grade 2 prior to Day 21, restart lenalidomide at next lower dose level and restart anti-coagulation.
Rash (non-blistering)	\geq Grade 3	
 • Hold (interrupt) lenalidomide for remainder of cycle • Reduce lenalidomide by 1 dose level and restart next cycle.
Rash	Grade 4 non-blistering or desquamating (blistering) any Grade	
 • Discontinue lenalidomide and take patient off study
Erythema multiforme	\geq Grade 3	
 • Discontinue lenalidomide and take patient off study
Hyperthyroidism or Hypothyroidism	Any grade	
 • Omit lenalidomide remainder of cycle • Evaluate etiology and initiate appropriate therapy • Restart lenalidomide at same dose level.
Sinus bradycardia/ other cardiac arrhythmia	Grade ≥ 2	
 • Hold (interrupt) lenalidomide for remainder of cycle. Follow at least weekly. • Reduce lenalidomide by 1 dose level and restart next cycle.
Sinus bradycardia/ other cardiac arrhythmia	\geq Grade 3	
 • Discontinue lenalidomide and take patient off study

Toxicity	NCI Toxicity Grade	Action
Allergic reaction or hypersensitivity	≥ Grade 2	
 • Hold (interrupt) lenalidomide for remainder of cycle. Follow at least weekly. • Reduce lenalidomide by 1 dose level and restart next cycle.
Allergic reaction or hypersensitivity	≥ Grade 3	
 • Discontinue lenalidomide and take patient off study
Venous thrombosis/embolism	≥ Grade 3	
 • Hold (interrupt) lenalidomide and Start anticoagulation; restart lenalidomide at investigator's discretion (maintain dose level).
Diarrhea	≥ Grade 3	
 • Hold (interrupt) clarithromycin until ≤ grade 1, then reduce dose to 250 mg twice daily
Dyspepsia	≥ Grade 3	
 • Hold (interrupt) clarithromycin and dexamethasone dosing until ≤ grade 1 • Reduce dexamethasone OR clarithromycin by 1 dose level based on attribution and restart dexamethasone and clarithromycin
Anaphylaxis or Hepatic failure	≥ Grade 3	
 • Discontinue clarithromycin and patient is off study
Loss of appetite or Nausea	≥ Grade 3	
 • Hold (interrupt) clarithromycin until ≤ grade 1, then reduce dose to 250 mg twice daily
Gastritis, gastric or duodenal ulcer	≥ Grade 3	
 • Hold (interrupt) dexamethasone until ≤ grade 1 • Reduce dexamethasone by 1 dose level and restart
Edema	≥ Grade 3	
 • Reduce dexamethasone by 1 dose level • Use diuretics as needed
Confusion or mood alternations	≥ Grade 2	
 • Hold (interrupt) dexamethasone until ≤ grade 1 • Reduce dexamethasone by 1 dose level and restart
Muscle weakness	≥ Grade 3	
 • Reduce dexamethasone by 1 dose level • If symptoms persist continue to reduce dexamethasone by 1 dose level as needed.

Toxicity	NCI Toxicity Grade	Action
Hyperglycemia	≥ Grade 3	
 Reduce dexamethasone by 1 dose level Treat with insulin or oral hypoglycemics as needed
Acute pancreatitis	≥ Grade 3	
 Discontinue dexamethasone and patient off study.
Other non-hematologic toxicity assessed as treatment-related	≥ Grade 3	
 Attribute toxicity to one or more drugs. Hold drug(s) attributed to toxicity for remainder of cycle. Reduce drug(s) attributed to toxicity by 1 dose level.*

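### Tables 2a and 2b leave the lenalidomide reduce-and-restart rows without an upper grade limit, so arrhythmia Grades 3–4 and hypersensitivity Grade 3 carry two opposite actions

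*Combined protocol and SAP*

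**What the plan says.** Section 9.6 makes the tables binding for related events: "Doses must be adjusted for adverse events deemed related to study drug by the investigator". The lenalidomide rows at issue are the same in Table 2a (Rd) and Table 2b (BiRd).

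- **Arrhythmia.** The ≥Grade 2 row reads "Hold (interrupt) lenalidomide for remainder of cycle. Follow at least weekly", then "Reduce lenalidomide by 1 dose level and restart next cycle". The next row, ≥Grade 3, reads "Discontinue lenalidomide and take patient off study".
- **Hypersensitivity.** The lower row is triggered by "Allergic reaction or hypersensitivity ≥ Grade 2" and carries the same hold, reduce and restart actions. The next row, ≥Grade 3, takes the patient off study.
- **Rash.** Non-blistering rash ≥Grade 3 is held for the rest of the cycle, then reduced and restarted. The off-study row is triggered by "Grade 4 non-blistering or desquamating (blistering) any Grade".

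Three other provisions bear on the point.

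- Section 9.5 requires drug-related events to have settled to Grade 2 or lower before a new cycle, and takes the patient off study if that needs more than four weeks. Where a drug was omitted for the rest of the previous cycle, it says "then the new cycle will be started with dose modifications as described in Section 9.6 and Table 2".
- Section 10.11 names Grade 4 skin toxicity and Grade 4 hypersensitivity as grounds for removal. It adds general criteria for excessive toxicity and for events that the investigator judges could cause serious or lasting harm.
- Table 2b also has a clarithromycin row that takes the patient off study for anaphylaxis or hepatic failure of Grade 3 or above.

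**The concern.** An open-ended ≥ in the lower row includes every grade in the higher row. A Grade 3 arrhythmia meets both triggers. One row says to restart lenalidomide at a lower dose in the next cycle; the other says to stop it for good and end participation. Neither 9.5 nor 9.6 says which row takes precedence.

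What is at stake is consistent handling of a severe event under a mandatory rule. Arrhythmia is a foreseeable concern here: subjects are at least 65, the Schedule of Assessments lists an electrocardiogram at screening only, and section 9.3.5 discourages QTc-altering agents, particularly with clarithromycin. Randomization is blocked by participating site, so more than one team would have to infer the same answer.

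**Working it through.** No sample size, power or event count enters this point, and the plan states no figure to reproduce. The check compares the grades that trigger each row, then looks for a provision that decides between the rows. Grades 1–4 are used; Grade 5 is death.

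**Step 1: overlaps within one table, and what 10.11 settles by name.**

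| Toxicity | Reduce row | Off-study row | In both | Named in 10.11 | Left |
|---|---|---|---|---|---|
| Arrhythmia | 2, 3, 4 | 3, 4 | 3, 4 | none | 3, 4 |
| Hypersensitivity | 2, 3, 4 | 3, 4 | 3, 4 | 4 | 3 |
| Non-blistering rash | 3, 4 | 4 | 4 | 4 | none |

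- Overlapping combinations: 2 + 2 + 1 = 5 per table.
- Settled by 10.11: 0 + 1 + 1 = 2 per table.
- Left: 5 − 2 = 3 per table.

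Over two tables this is 10 overlaps, 4 settled and 6 left. Because the lenalidomide rows match, the six are three distinct combinations, each appearing twice.

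**Step 2: is there another tie-break for the three?**

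- *Section 9.6* makes the actions mandatory for related events and gives no order of precedence.
- *Section 9.5* sets the condition for starting a cycle and then refers back to 9.6 and Table 2. A Grade 3 arrhythmia that was held and has come down to Grade 2 or lower meets that condition, so 9.5 does not exclude the restart row.
- *The general criteria in 10.11* allow removal on judgment. They do not choose between the rows.
- *The Table 2b clarithromycin row* removes BiRd patients with anaphylaxis ≥Grade 3. It covers one form of Grade 3 hypersensitivity in one arm. It does not reach other Grade 3 hypersensitivity, any such event in the Rd arm, or arrhythmia.

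**Step 3: how far apart are the two actions?** Both stop lenalidomide at once. They part at the next cycle, which 9.5 does not allow until the event is Grade 2 or lower. The difference is a reduced-dose restart after resolution against permanent discontinuation.

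**Step 4: do bounded cells work?** With the lower rows set to Grade 2, Grade 2 and Grade 3, the pairs become {2} and {3, 4} for arrhythmia, {2} and {3, 4} for hypersensitivity, and {3} and {4} for non-blistering rash. The overlap is zero, and every grade covered now still falls under one row.

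**The case against.** The strongest reply is that the tables resolve themselves. The rows ascend by grade, and if the lower arrhythmia row governed Grades 3 and 4, the ≥Grade 3 row would never operate; the same logic applies to hypersensitivity. With the immediate hold and the 9.5 condition, little harm could follow from the laxer reading. This stands as a limit on weight. It does not remove the contradiction, because the reader must supply the precedence.

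Stronger readings are tempting, and the documents do not support them.

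- *Patients could be restarted after Grade 4 rash or Grade 4 hypersensitivity.* Section 10.11 removes both, whichever row is read.
- *Lenalidomide could be restarted during an unresolved Grade 3–4 event.* Section 9.5 forbids starting the cycle.
- *By naming only Grade 4 hypersensitivity, 10.11 endorses restart at Grade 3.* The inference is weak. Section 10.11 also omits other off-study events in the tables, such as pancreatitis and hepatic failure, so it is not a complete list.
- *Section 10.11 contradicts the tables on lower-grade skin events and must be rewritten to match.* The off-study rows operate on their own, so a shorter list in 10.11 does not cancel them.
- *The overlap biases PFS or the comparison of arms.* The lenalidomide rows are the same in both arms and the documents give no rates for these events. Nothing supports a direction or a size.

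**Conclusion.** The point holds as a minor contradiction in a mandatory safety rule. Three toxicity-grade combinations, repeated in two tables, carry opposite instructions: arrhythmia Grade 3, arrhythmia Grade 4 and hypersensitivity Grade 3. None has a specific tie-break, apart from the anaphylaxis row in Table 2b. The two Grade 4 overlaps for rash and hypersensitivity are drafting slips without consequence, because 10.11 decides them.

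The residual risk is re-exposure to lenalidomide at a reduced dose after a severe event has resolved, at a site that follows the lower row. The conclusion assumes that ≥ means what it says and that the event is judged related to study drug, which is when 9.6 requires action. No number of affected patients can be given.

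**What to change.** In both tables, change the grade cell of the reduce-and-restart row to:

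- Grade 2 for arrhythmia;
- Grade 2 for allergic reaction or hypersensitivity;
- Grade 3 for non-blistering rash.

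The discontinue rows then govern all higher grades alone. The cost is six table cells (three in each table), with no added visits, procedures or patients.

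Leave the skin and hypersensitivity sentence in 10.11 as it is. Section 10.11 has no attribution condition, whereas 9.6 ties mandatory action to events judged related to study drug. Copying the table thresholds into 10.11 would force removal for lower-grade events of any cause, including a reaction to the Bactrim prophylaxis that 9.4 directs. Such removals would count as EFS events under section 2.2 and be censored in the primary PFS analysis (Table A). At most, add one cross-reference in 10.11 stating that drug-related events with an off-study action in Tables 2a or 2b are also grounds for removal.

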MRD: Minimal residual disease testing will be performed in subjects who achieve complete response. MRD testing may be performed either by flow cytometry or PCR, whichever is more readily available at the study institution.

Subjects will continue their randomized treatment assignment until disease progression or unacceptable toxicity (whichever occurs first). In case toxicity precludes dosing of one agent (i.e dexamethasone, clarithromycin, lenalidomide), treatment regimen will continue with the remaining agents. Subjects unable to receive ALL the components of the assigned treatment arms will be removed from study after reasonable attempts to dose reduce and manage side effects. Subjects with elevations of AST/ALT greater than three times the upper limit of normal, with concomitant elevation of bilirubin 2 times the upper limit of normal, not attributable to disease, should be discontinued from treatment. Subjects can also be removed from study at investigator's discretion, or if they withdraw consent. At completion or early discontinuation of treatment, subjects will be followed for 30 additional days or up to the initiation of subsequent treatment (whichever occurs first), after which they will be off the active treatment phase of the study. Long term follow up for disease status and survival will proceed until the subject has withdrawn consent, is lost to follow up, or has died.

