14.0 STATISTICAL CONSIDERATIONS

14.1 Study Design/Primary Endpoint

The study is a randomized phase III design, and the primary endpoint in both treatment arms is median PFS. PFS will be defined as the time from randomization day until objective progression or death from any cause. The PFS distributions of the two treatment arms will be estimated by Kaplan-Meier survival analysis and the PFS distributions will be compared by an unstratified log-rank test. Ninety-five percent confidence intervals for the Kaplan-Meier PFS estimates will be calculated using

Greenwood's formulae. The primary comparison will be made using the intent-to-treat (ITT) patient population. Patients will be analyzed based on their randomization assignments, regardless of therapy initiation or compliance. A secondary analysis will be performed comparing "evaluable" patients as patients who met eligibility requirements, have initiated therapy, and were not removed from the study for non-compliance or patient withdrawal.

The median PFS for MM patients receiving Revlimid /dexamethasone chemotherapy (Rd) (Arm A) is expected to be approximately 25.5 months, as reported in the MM-010 study of continuous Rd vs Rd for 18 months (Facon T, Dimopoulos M, Dispenzieri A, et al: Initial phase 3 results of the FIRST trial in newly diagnosed multiple myeloma patients ineligible for stem cell transplant. 2013 ASH Annual Meeting. Abstract 2. Presented December 8, 2013.). Therefore, the target median PFS for patients receiving Revlimid/dexamethasone/Clarithromycin (BiRd) (Arm B) is hypothesized to be 44.6 months (target hazard ratio = 1.75).

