14.3 Analysis of Progression-Free Survival

Because the analysis of PFS can be difficult, especially in the presence of missing data and lost-to-follow-up, sensitivity analyses can be helpful in determining whether the PFS analysis is robust. As suggested by the alternative PFS definitions recommended in the FDA's Guidance for Industry, "Clinical Trial Endpoints for the Approval of Cancer Drugs and Biologics (May, 2007), the following three types of PFS analyses will be

conducted:

Table A. PFS #1 (includes documented progression only) (Primary PFS Analysis):

Situation	Date of Progression or Censoring	Outcome
No baseline tumor assessments	Randomization	Censored
Progression documented between scheduled visits	Earliest of: 
 • Date of hematological assessment showing progression; or • Date of radiological assessment showing progression; or • Date of urine assessment showing progression 	Progressed
No progression	Date of last hematological, radiological, or urine assessment	Censored
Treatment discontinuation for undocumented progression	Date of last hematological, radiological, or urine assessment	Censored
Treatment discontinuation for toxicity or other reason	Date of last hematological, radiological, or urine assessment	Censored
New anticancer treatment started	Date of last hematological, radiological, or urine assessment	Censored
Death before first PD assessment	Date of death	Progressed
Death between adequate assessment visits	Date of death	Progressed
Death or progression after more than one missed visit	If progression: 
 • Date of hematological assessment showing progression; or • Date of radiological assessment showing progression; or • Date of urine assessment showing progression OR, if not progression: Date of last hematological, radiological, or urine assessment	Censored

Table A represents the primary PFS analysis that only includes well-documented and verifiable progression events. Other data are censored. In Table A, the progression dates are 1) based only on radiological assessments verified by an IRC (clinical progression will not be considered a progression endpoint), 2) assigned to the first time when disease progression is noted, and 3) the date of death when the patient is closely followed. However, deaths occurring after two or missed visits will be censored at the last visit.

Table B. PFS #2 (uniform progression and assessment dates) (PFS Sensitivity Analysis #1):

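### Tables A, B and C all censor PFS when treatment stops for toxicity or another reason, and no planned PFS analysis tests whether that matters

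*Combined protocol and SAP*

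**What the plan says.** Section 14.1 sets the endpoint: "PFS will be defined as the time from randomization day until objective progression or death from any cause". For the primary population it adds: "Patients will be analyzed based on their randomization assignments, regardless of therapy initiation or compliance".

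Section 14.3 then gives three sets of censoring rules. Table A is labelled primary; Tables B and C are sensitivity analyses. All three have a row headed "Treatment discontinuation for toxicity or other reason" with the outcome censored, at the last hematological, radiological or urine assessment (Table A) or the last adequately assessed visit (Tables B and C). All three also censor when new anticancer treatment starts; Table C does so only where progression has not been claimed.

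Section 14.3 re-runs the tables with one change: deaths or progressions after more than one missed visit become events. It also plans a comparison of follow-up adequacy by arm and the Freidlin-Korn method for evaluation-time bias.

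Section 10.4 plans to follow patients to progression or death after they leave the study. Follow-up is monthly to bi-monthly in clinic, or by six-monthly contact for those who do not return to clinic.

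On removal for toxicity, Section 4.1 says: "In case toxicity precludes dosing of one agent (i.e dexamethasone, clarithromycin, lenalidomide), treatment regimen will continue with the remaining agents". In Table 2b (BiRd, Section 9.6) the arrhythmia and allergic-reaction rows name only lenalidomide. From Grade 2 it is held and reduced; from Grade 3 the instruction is "Discontinue lenalidomide and take patient off study". Table 2a (Rd) has the same rows.

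**The concern.** Read alone, Section 14.1 counts a progression that happens after treatment has stopped. Table A, as written, does not. That is safe only if patients who stop have the same later risk of progression as those who continue, within each arm. Patients who stop for toxicity may be frailer, and the arms may differ in how many stop, because BiRd adds clarithromycin to the same backbone. Treatment is open-label, and Section 10.11 also allows removal at the investigator's judgment.

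Sensitivity analyses exist to vary a doubtful assumption. Tables B and C vary the dating of events and the use of investigator claims, but keep this censoring rule. If all three agree, that says nothing about whether the rule shaped the result, even though the follow-up needed to check it is already planned.

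**Working it through.** **1. Which planned analysis varies the rule?**

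| Analysis | Progression after stopping for toxicity |
|---|---|
| Table A (primary) | Censored at last assessment |
| Table B | Censored at last adequate visit |
| Table C | Censored at last adequate visit |
| Re-run of A to C | Changed only if after more than one missed visit |
| Freidlin-Korn method | Addresses assessment timing, not this rule |
| Evaluable-patient analysis (14.1) | Removes patients; restores no follow-up |
| EFS (2.2) | Coming off protocol is itself the event; descriptive |
| OS, PFS2 | Different endpoints; PFS2 descriptive |

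None is designed to count these later progressions in PFS.

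**2. The plan's own figure.** Inputs from Section 14.2: medians 25.5 and 44.6 months, hazard ratio (control over experimental) 1.75, two-sided 0.05, 90% power, 36 months' accrual plus 12 months' follow-up, no dropouts. Schoenfeld: 4 × (1.960 + 1.282)² / (ln 1.75)² = 134.2 events, within 3% of the stated 133. Power at 133 events is 89.7%.

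Hazards are ln 2/25.5 = 0.02718 and ln 2/44.6 = 0.01554 per month. By month 48 with uniform accrual the event probabilities are 0.540 and 0.364, so 306 patients give 153 × (0.540 + 0.364) = 138 events.

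**3. Effect on event numbers.** The documents give no toxicity-discontinuation rate, so these annual rates, equal in both arms, are assumptions. With monthly censoring rate m = −ln(1 − annual rate)/12 and t = λ + m, the event probability is (λ/t) × [1 − (e^(−12t) − e^(−48t))/(36t)].

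| Assumed rate per year | Events, N = 306 | Power | Events, N = 337 | Power |
|---|---|---|---|---|
| 0% | 138 | 91% | 152 | 93% |
| 5% | 130 | 89% | 144 | 92% |
| 10% | 123 | 87% | 135 | 90% |
| 15% | 115 | 85% | 127 | 88% |
| 20% | 108 | 83% | 119 | 86% |

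Both totals appear because Section 4.1 gives 306 and Section 14.2 gives 337 after dropout. If the analysis waits for 133 events, the loss is time rather than power.

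**4. Effect on the comparison.** This null simulation assumes no treatment effect, 306 patients, a base hazard of ln 2/25.5, and 30% frail patients with k times that hazard. Toxicity censoring falls on the frail only, at 10% a year on Rd and 30% or 50% on BiRd. As a share of all patients in year one, ignoring progression, that is 0.3 × 10% = 3% on Rd against 9% or 15% on BiRd. There were 1,500 trials per setting. The hazard ratio here is BiRd over Rd, and the nominal false-positive rate in favour of BiRd is 2.5%.

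| k | BiRd rate | HR with censoring | False positives |
|---|---|---|---|
| 1 (non-informative) | 30% / 50% | 0.99 / 1.00 | 2.5% / 3.0% |
| 1.5 | 30% / 50% | 0.99 / 0.97 | 3.3% / 4.5% |
| 2 | 30% / 50% | 0.98 / 0.94 | 3.3% / 4.9% |
| 3 | 30% / 50% | 0.96 / 0.93 | 4.8% / 6.9% |

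When the same patients were followed through, the average ratio was 0.99 to 1.01 in every setting and false positives were 1.8% to 3.1%. With equal censoring in both arms (10% a year), k up to 3 produced no shift (2.1% to 2.5%). The simulation error on a 2.5% rate is √(0.025 × 0.975/1,500) = 0.4 percentage points. Distortion therefore needs both a difference between arms and a link to prognosis.

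**The case against.** The strongest reply is that the censoring is prespecified, applies to both arms, and follows alternative definitions that Section 14.3 takes from regulatory guidance. That stands as a reason to leave Table A as primary. It does not explain why neither sensitivity table relaxes the rule.

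A second reply is that some later events may be counted anyway. The tables give no precedence between rows, so a documented progression or a death after stopping fits two rows, and the re-run may catch patients who missed visits. This is fair. It means one should not infer that such events can never count, only that no analysis is built to count them. The comparison of follow-up adequacy may also expose an imbalance, but it does not re-estimate the effect.

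A reader might go further and infer from Table 2b that a Grade 3 reaction attributed to clarithromycin has no defined handling, so that patients are removed at will in one arm. The documents do not support that. Section 9.6 says that "the toxicity should be attributed to one or more drugs in the BiRD regimen and dose modifications instituted as instructed", and the Grade 3 rows carry no attribution condition, so read literally they give one answer: off study. Section 9.6 also makes continuing the other drugs the default unless a row notes otherwise. The catch-all ("Attribute toxicity to one or more drugs. Hold drug(s) attributed to toxicity for remainder of cycle") is for toxicities not listed, and these are listed. Table 2a removes Rd patients at the same grade, so the rule itself is even-handed. Keeping such patients on lenalidomide and dexamethasone would be a debatable clinical choice and would end that parity.

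What remains is wording. Section 4.1 would continue the other agents, and its next sentence, "Subjects unable to receive ALL the components of the assigned treatment arms will be removed from study after reasonable attempts to dose reduce", can mean unable to take any component or unable to take every component. Nothing says expressly that Table 2b prevails over Section 4.1. The numerical stake is small. If an assumed 10% of 153 BiRd patients (15) reacted in months 0 to 6 and then progressed at the Rd rate, censoring them all would move the hazard ratio (control over experimental) from 1.655 to 1.749. That is ln(1.749/1.655)/0.173 = 0.32 of a standard error, where 0.173 = 2/√133. At 1% of patients it is 0.03, and if they progress at the BiRd rate there is no gap.

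**Conclusion.** The censoring point holds and is minor. The primary analysis departs from the Section 14.1 definition for every discontinuation for toxicity or other reason, in both arms, and no planned PFS analysis tests that departure.

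Neither the size nor the direction of any effect can be determined from the documents. The event counts and false-positive rates above rest on assumed discontinuation rates, an assumed frail group and, for the bias, assumed imbalance against BiRd. If the patients who stop on BiRd were instead those at lower risk, the shift would go the other way. A reader might infer that the trial is biased towards BiRd or underpowered; neither follows. The finding is an untested assumption that is cheap to test.

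The Table 2b matter is a secondary clarification and not a source of demonstrated bias.

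**What to change.** 1. Keep Table A as primary. Add one ITT sensitivity analysis of PFS that follows Section 14.1:
   - Do not censor at discontinuation for toxicity or other reason.
   - For those patients, do not censor at new anticancer treatment either; otherwise anyone who moves to another therapy is still lost.
   - Count later documented progression or death from the Section 10.4 follow-up.
2. Report by arm how many patients stopped for toxicity, and how many of them then had clinic follow-up or six-monthly contact only.
3. State whether the BiRd arrhythmia and allergic-reaction rows override Section 4.1 when the event is attributed to clarithromycin. The rash and erythema multiforme rows are worded the same way, so the sentence should cover them too. Which rule prevails is a clinical decision for the sponsor.

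The cost is one extra analysis, one table by arm and one clarifying sentence, with no added patients, visits or tests. The drawback is that progression dates after leaving the study will be less precise, especially with six-monthly contact, so the added analysis should stay supportive.
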